## STUDY PROTOCOL

### 1. Rationale

**(a) Statement of the Problem:** Post-9/11 Veterans who served in OEF/OIF face many challenges as they re-enter civilian life after structured military careers. Yet, underutilization and resistance to mental health treatment remains a significant problem [3-5]. Recent investigations of community reintegration problems among returning Veterans found that half of combat Veterans who use Veterans Administration (VA) services reported difficulty in readjusting to civilian life, including difficulty in social functioning, productivity in work and school settings, community involvement, and self-care domains [6, 7]. High rates of marital, family, and cohabitation discord were reported, with 75% reporting a family conflict in the last week [8]. At least one-third reported divorce, dangerous driving and risky behaviors, increased substance use, and impulsivity and anger control problems since deployment. Almost all Veterans expressed interest in receiving services to help readjust to civilian life, and receiving reintegration services at a VA facility was reported as the preferred way to receive help. Mental health and anger problems are often cited as driving Veterans' difficulties readjusting to civilian life. Anger is becoming more widely recognized for its involvement in the psychological adjustment problems of post-9/11 Veterans [9]. Research has shown that anger directly influences treatment outcome [10]. In fact, history of untreated PTSD and aggression have been demonstrated to be pervasive among post-9/11 Veterans who die by suicide in the months before death [11]. Veterans with probable PTSD report more reintegration and anger problems, and greater interest in services than Veterans without [6]. Reintegration and anger problems continue for years post-combat and may not resolve without intervention [7].

\*In February 2023, we received approval for a 1-year cost extension to continue this study for one additional year; the study end date is now 3/31/24 instead of 3/31/23. Any relevant changes to the study protocol resulting from this timeline extension are outlined below, where appropriate.

#### **Phase 1:** Years 1 and 2

We will initiate the study at the Boston VAMC and develop Standard Operating Procedures for the addition of site 2 in Phase 2.

#### **Phase 2:** Years 3, 4, and 5

We will initiate the study at the second site, the Houston VAMC, in Year 3. We have obtained IRB approval to initiate site 2 from the Houston VA (see attached documentation of approval by Michael E. DeBakey Medical Center IRB). Given the transition to telehealth workshops, we now plan to initiate recruitment only for Veterans through site 2 (Houston) during Years 3, 4, and 5.

In-person workshops may be initiated at site 2 (with appropriate IRB approvals) in the future.

### (b) Hypotheses & Aims

#### **Primary Aim 1. Examine treatment effects of STEP-Home on primary outcomes relative to Present Centered Group Therapy (PCGT):**

***Hypothesis 1A. Participants randomized into the STEP-Home intervention will show improvement on reintegration, readjustment, and anger post-intervention (expressed by lower scores; less difficulty).*** Military to Civilian Questionnaire (M2CQ), Post-Deployment Readjustment Inventory (PDRI), and State-Trait Anger Expression Inventory (STAXI-2) scores post-intervention (T4) < baseline (T1)

***Hypothesis 1B. Participants randomized into STEP-Home will show greater improvement in primary outcomes as compared to PCGT.***

Change scores baseline (T1) to post-intervention (T4) STEP-Home > PCGT change scores

Post-intervention (T4) primary outcome scores STEP-Home < PCGT primary outcome scores (T4)

**Primary Aim 2. Examine maintenance of treatment effects on primary outcomes:**

***Hypothesis 2: Treatment effects will be maintained at follow up in both groups.***

Differential treatment effect of STEP-Home over PCGT post-intervention (T4) will be maintained at follow up (T5)

**Exploratory Aim 1. Explore treatment effects of STEP-Home on measures of mental health, functional and vocational status and cognitive secondary outcomes targeted indirectly in the workshop.**

**Exploratory Aim 2. Acquisition of core skills (problem solving, emotional regulation, attention training) will mediate the effect of treatment on primary outcomes post-intervention and at follow up.**

## **2. Background and Significance**

**(a) Background:** The unique and challenging needs of post-9/11 Veterans necessitate the development of novel, empirically validated, skill-based, integrative interventions for civilian reintegration that are cost-effective and can be easily implemented across the VA system. Returning Veterans face high rates of reintegration difficulties that continue for years post-deployment and may not resolve without intervention [6]. We have described this cohort as “multi-morbid” [36]. Attempting to care for such complicated patients with single modality treatments has had limited success [29-31, 37, 38] and integrated transdiagnostic treatments for this cohort are quite limited [39-41]. Those that do exist are designed for Veterans meeting multiple clinical diagnoses and may not be appropriate for the broad range of Veterans STEP-Home is designed to help. We are not aware of any skills-based program that seeks to help all Veterans (with or without clinical diagnoses) reintegrate into civilian life. Research on TBI in post-9/11 Veterans [42, 43] underscores the need for programs that utilize an interdisciplinary approach to reintegration. Programs designed to address challenges of Veterans as they reintegrate in vocational environments, particularly integrative approaches, are greatly needed [44]. The STEP-Home intervention provides such a program. STEP-Home includes focused cognitive and emotional regulation skills training and is informed by the most recent research with returning Veterans and available programs focused on reintegration in VA and military settings (e.g., Battlemind training [45]).

**(b) Significance:** In this proposal, we extend our previous SPIRE feasibility and preliminary effectiveness study to examine STEP-Home efficacy in a RCT design. This novel therapy will target the specific needs of a broad range of underserved post-9/11 Veterans. It is designed to foster reintegration by facilitating meaningful improvement in the functional skills most central to community participation: emotional regulation (ER), problem solving (PS), and attention functioning (AT). The skills trained in the STEP-Home workshop are novel in their collective use and have not been systematically applied to a Veteran population prior to our SPIRE study. STEP-Home will equip Veterans with skills to improve daily function, reduce anger and irritability, and assist reintegration to civilian life through return to work, family, and community, while simultaneously providing psychoeducation to promote future engagement in VA care.

The innovative nature of the STEP-Home intervention is founded in the fact that it is: (a) an adaptation of an established and efficacious intervention [2, 46, 47] now applied to post-9/11 Veterans; (b) nonstigmatizing (not “therapy” but a “skills workshop” to boost acceptance, adherence and retention); (c) transdiagnostic (open to all post-9/11 Veterans with self-reported reintegration difficulties; Veterans often have multiple mental health diagnoses, but it is not required for enrollment); (d) integrative (focus on the whole person rather than specific and often stigmatizing mental and physical health conditions); (e) comprised of Veteran-specific content to teach participants cognitive behavioral skills needed for successful reintegration (which led to greater acceptability in feasibility study); (f) targets anger and irritability, particularly during interactions with civilians; (g) emphasizes psychoeducation (including other available treatment options for common mental health conditions); and (h) challenges beliefs/barriers to mental health care to increase openness to future treatment and greater mental health treatment utilization. Many Veterans who participated in the development phases of this workshop have gone on to trauma or other focused therapies, or taken on vocational (work/school/volunteer) roles after STEP-Home.

We have demonstrated that the STEP-Home workshop is feasible and results in pre-post change in core skill acquisition that we demonstrated to be directly associated with post-workshop improvement in reintegration status in our SPiRE study. Given the many comorbidities of this cohort, our innovative treatment addresses multiple aspects of mental health, cognitive, and emotional function simultaneously and bolsters reintegration in a short-term group to maximize cost-effectiveness while maintaining quality of care [48].

**(c) Relevance to Veterans Health:** The successful completion of the aims proposed has the potential to significantly improve skills to foster civilian reintegration in post-9/11 Veterans. Furthermore, the STEP-Home SPiRE feasibility study demonstrated that the workshop also serves as a gateway for Veterans who are hesitant to participate in traditional mental health treatments to promote openness and engagement in additional, critically needed, VA services. Given the high rate of treatment resistance in this cohort, developing acceptable interventions that promote treatment engagement and retention, and open the door to future VA care, is necessary to improve functional status and to reduce long-term healthcare costs of untreated mental health illnesses.

### **3. Work Accomplished**

Data from our successful SPiRE feasibility and preliminary effectiveness study [10] has demonstrated: (1) STEP-Home was acceptable in this Veteran cohort; and (2) the change in treatment related skill acquisition was associated with improved community reintegration status (as measured by the Military to Civilian Questionnaire; M2CQ) post-workshop. Critically, the dropout rate for the STEP-Home workshop was less than half that observed in standard psychological treatment for PTSD in post-9/11 Veterans [11]. Data also demonstrated that STEP-Home functions as a gateway by increasing engagement in both vocational activities and critically needed mental health treatments at VA for Veterans hesitant to seek help. STEP-Home offers a much needed, palatable, and minimally stigmatizing intervention for post-9/11 Veterans struggling with reintegration difficulties that is feasible, acceptable, and has shown preliminary effectiveness.

### **4. Work Proposed**

**(a) Study Objectives:** There are two major experimental objectives to this project: (1) To examine treatment effects of STEP-Home on primary outcomes relative to Present Centered Group Therapy (PCGT); (2) To examine maintenance of treatment effects on primary outcomes; and two exploratory aims: (1) To examine treatment effects on secondary outcomes targeted indirectly in the workshop; (2) To determine if acquisition of core skills or “key ingredients” mediates primary outcomes. In February 2023, we received approval for a 1-year cost extension to continue this study for one additional year; the study end date is now 3/31/24 instead of 3/31/23. Therefore, the objectives listed above will be accomplished across a 5-year timeline, instead of the original 4-year timeline.

**(b) Study Design (Phase 1):** We will conduct a randomized control trial (RCT) of STEP-Home at the VA Boston Healthcare System, Jamaica Plain campus and the Michael E. DeBakey Medical Center in Houston. With the 1-year study extension approved in February 2023, our funded aims have been updated to enroll 144 Veterans in Boston (original enrollment number was 112 in Boston) and 96 in Houston for a total of 240 participants. In order to achieve this, given drop out, we will recruit 300 Veterans overall, when accounting for participants at both sites.

[figure not shown]
Recruitment will be conducted in Boston (Years 1-5) and Houston (Years 3-5). Beginning in Year 3, Houston TRACTS/STEP-Home staff will assist in recruitment and referrals. The Houston site will assist with any clinical and/or safety concerns for Houston Veterans under the leadership of site PI, [name], a licensed psychiatrist with ample experience in this arena in coordination with Boston and study PI, [name]. All study procedures across both sites will be reviewed by our Data Safety Monitoring Board and reported to local IRBs at both sites.

Participants will be randomly assigned to receive one of the two group interventions: STEP-Home or PCGT, and each intervention will meet one time a week for 12 weeks. We will use statistical software to conduct cluster randomization to assign veterans to the intervention group. We do not plan to use matching or stratified

randomization to balance the interventions on patient characteristics (e.g. age, prevalence of traumatic brain injury and psychiatric conditions, etc.) since we do not have any a priori reason to expect that such factors will significantly influence our primary outcomes. We will assess any patient characteristics as possible confounders in our analyses if they differ across groups (see Analytic Plan below). Given the group treatment modality for both conditions, it will be necessary to accrue participants for a cohort before randomization and treatment can begin. Each cohort will include a minimum of 8 and a maximum of 20 participants who will be randomized to either STEP-Home (n=4-10 Veterans per treatment group) or PCGT (n=4-10 Veterans per active control). The treatment group and active control group will be matched in size (n's equal at randomization) and populated based on recruitment success. The goal will be to recruit 16 Veterans and randomize to two groups of 8. However, if recruitment is slow, the smallest randomization pool allowed will be 8 (4 Veterans assigned to each group). If recruitment is ahead of pace, the largest randomization pool allowed will be 20 (10 Veterans assigned to each group).

When a cohort large enough is available, randomization into STEP-Home or PCGT will occur and participation in the study begins (i.e., Time 1; T1: Pre), during which we will consent, administer the baseline assessments, randomly assign to either the STEP-Home or the PCGT arm, and schedule the treatment sessions. All participants will be assessed at the following 5 outcome points: Screening, at randomization (T1: Assessment), during treatment 4-week skills check (T2: Brief Skills Check), during treatment 8-week skills check (T3: Brief Skills Check), post-intervention (T4: Assessment), and at 3-months follow up (T5: Assessment). Assessments and skills checks are all self-report; therefore, blinded assessors are not required. Participants who decide to leave the program early will be asked to complete all assessments via secure Qualtrics link sent in MyHealtheVet or via postal mail service according to the RCT timeline following the intent-to-treat format, but will not be required to do so. Veterans will participate in their assigned treatment arm 1 day/week for approximately 2 hours. Replicating our SPiRE feasibility and preliminary effectiveness study [1], staff members will work in pairs when running groups. These same two staff members will offer to meet individually with Veterans before or after group approximately 4 to 6 times/workshop; it will be the Veterans' choice whether they participate in these individual meetings.

Assessments (T1, T4, and T5) may be done in person or online (see Data Security Section for description of Qualtrics online data entry). Brief Skills Checks (T2 & T3) may also be done in person or online.

**Randomization Figure.** T1 = Baseline Assessment; T2 = 4-week Skills check; T3 = 8-week Skills check; T4 = 12-week Post-Intervention Assessment; T5 = 24-week Follow-up Assessment.

- Assessments = T1, T4, and T5; Reimbursement = \$20
- Brief Skills Checks = T2 & T3; Reimbursement = \$0

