### **(1) Primary Outcome Measures**

The primary outcome measures may include the following assessments:

- Military to Civilian Questionnaire (M2C-Q): A 16-item measure of post-deployment community reintegration in post-9/11 Veterans that assesses six domains (interpersonal relationships, productivity at work, school or home, community participation, self-care, leisure, and perceived meaning of life).
- Post-Deployment Readjustment Inventory (PDRI): A 36-item measure of readjustment in post-9/11 Veterans with six subscales (career challenges, social difficulties, intimate relationship problems, health concerns, concerns about deployment, and PTSD symptoms).
- State-Trait Anger Expression Inventory (STAXI-2): A 57-item widely used measure to assess state anger, trait anger, and anger expression with three subscales (trait anger, anger expression, and anger control).

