### Analytic Plan & Power Analysis

\* Analytic Plan & Power calculations may include references to the full study sample, including Phase 2 recruitment at site 2 (Houston).

\*\*The February 2023 project modification/1-year extension requested funds to complete Cohort 19 (ongoing at the time of the project modification request) and enroll one additional cohort (Cohort 20) to ensure sufficient power for Aim 1 (Hypotheses 1A, 1B) and Aim 2, and to support final data analysis and manuscript submission in the last 6 months of the 1-year cost extension (October 2023 – March 2024). Of note, the study's Aims, listed below, remain unchanged with the project modification. The only changes involve an increase in our targeted enrollment number, to ensure sufficient power, as enrollment and measures completion rates to date are slightly under our original goals.

Data Management. Data entered in the database will be verified and quality assurance procedures will be followed; Human Subjects (*Accuracy/ Integrity of Data*); Data management plan (“09\_VA\_DMAP”).

For continuous variables, the mean, median, standard deviation, minimum, maximum, interquartile range, and sample size for each intervention group will be reported at each time point. For categorical variables the frequency distribution will be reported for each treatment group.

Baseline Comparability. While no substantial differences between intervention groups are anticipated given randomization, we will use summary statistics, graphical techniques such as boxplots, and univariate analyses to compare baseline characteristics of groups. Pre-intervention values will be compared between

STEP-Home and PCGT groups using t-tests and chi-squared tests, as appropriate, to determine if the groups are balanced with respect to baseline characteristics. This comparison will allow us to identify potential confounders and moderators to be included in multivariate analyses. Clinical covariates include: age; education; diagnosis of TBI history; PTSD, mood disorder, anxiety, substance use, chronic pain, sleep quality.

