Statistical Methods by Research Aims. The primary analysis for each aim will use an intent-to-treat (ITT) approach (i.e., all randomized subjects will be used in the analysis). ITT is optimal since it provides the least biased estimate of the treatment effect and the randomization balances STEP-Home and PCGT groups on known and unknown baseline confounders. This approach is appropriate for the proposed study given an anticipated low attrition rate of ~17% (based on attrition rates observed in our SPiRE study and Mt. Sinai's STEP RCT). We will implement quality assurance procedures to minimize protocol deviations and ensure correct treatment assignment according to the randomization. As a sensitivity analysis, we will conduct a per-protocol analysis in the subset of participants who complete an adequate amount of treatment ( $\geq 80\%$  of weekly sessions). We will assess the assumptions of homogeneity of variance and normality of residuals for each regression model and apply an appropriate transformation of the outcome if needed. We will address missing data, under the assumption of missing at random, using multiple imputation. Any subject characteristics associated with both the treatment group and primary outcome measure will be adjusted for in the final statistical model as specified in each aim.

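### The plan discounts PTSD as an influence on the primary outcomes, against its own rationale, and lets baseline predictors into the Hypothesis 1B models only through chance imbalance

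*Combined protocol and SAP*

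**What the plan says.** Section 4, Work Proposed, (b) Study Design explains the absence of matching or stratified randomisation on characteristics such as age, TBI and psychiatric conditions: "since we do not have any a priori reason to expect that such factors will significantly influence our primary outcomes". It adds: "We will assess any patient characteristics as possible confounders in our analyses if they differ across groups".

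The Rationale, part (a), states that "Veterans with probable PTSD report more reintegration and anger problems". It also says that "Mental health and anger problems are often cited as driving" the trouble Veterans have in returning to civilian life. Reintegration, readjustment and anger are the three primary outcome domains. Under Primary Outcome Measures, the six PDRI subscales end with "health concerns, concerns about deployment, and PTSD symptoms".

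In the Analytic Plan, Baseline Comparability compares the arms by t-tests and chi-squared tests and says: "This comparison will allow us to identify potential confounders and moderators to be included in multivariate analyses". The candidates follow: "Clinical covariates include: age; education; diagnosis of TBI history; PTSD, mood disorder, anxiety, substance use, chronic pain, sleep quality". No significance threshold is given. Statistical Methods by Research Aims sets the entry rule: "Any subject characteristics associated with both the treatment group and primary outcome measure will be adjusted for in the final statistical model". Under Hypothesis 1B, the mixed model and the T4 regression adjust for whatever confounders this identifies. No covariate is prespecified for either model, and the T4 regression as described does not include the T1 score of the outcome. The schedule of measures has the PCL-5 at T1, T4 and T5.

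**The concern.** Two things do not fit together. The design section denies any prior reason to think psychiatric conditions matter for the primary outcomes. The Rationale supplies one for PTSD, and the PDRI contains PTSD symptoms by construction.

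The analysis rule then behaves as if the denial were true. A baseline measure that predicts outcome well but happens to be balanced between arms is left out, although adjusting for it would sharpen the treatment comparison. Because allocation is random, imbalance is chance alone, so the covariate set of a primary model is settled by chance after the data are in. At stake are precision in Hypothesis 1B and an analysis model that cannot be written down in advance. The Analytic Plan itself reports that enrollment and measures completion ran slightly below goal and that the extension was sought to secure power.

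**Working it through.** **1. The plan's own figure.** Power Analysis: d = 0.44, one-sided 0.05, 80% power, intraclass correlation 0.04, 20% attrition. Section 4(b): target group size 8.
- Two-sample t-test (noncentral t): 65 per arm, 130 in total.
- Design effect: 1 + (8 - 1) x 0.04 = 1.28.
- Total: 130 x 1.28 / 0.80 = 208.

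This matches the stated 208 exactly, so the plan's power assumes no covariate adjustment. The steps below use 65 effective participants per arm.

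**2. How often the rule admits a covariate.** The threshold is not stated; 0.05 two-sided is assumed. Each covariate then shows an arm difference in about 5% of trials. For at least one of the nine listed, treated as independent: 1 - 0.95^9 = 37%. In simulation, a single prognostic covariate passed both conditions in about 4.5-5.2% of trials.

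**3. T4 regression as written (1B.2, no T1 score).** The correlation r of T1 PCL-5 with the T4 score is not in the documents and is assumed. Prespecified adjustment multiplies residual variance by v = 1 - r^2, and the noncentrality is (0.44 / sqrt(v)) x sqrt(65/2) = 2.508 / sqrt(v). Power under the rule is by simulation.

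| r | v | Noncentrality | Power, PCL-5 prespecified | Power under the rule |
|---|---|---|---|---|
| 0 | 1.00 | 2.51 | 80% (unadjusted) | n/a |
| 0.4 | 0.84 | 2.74 | 86% | about 81% |
| 0.5 | 0.75 | 2.90 | 89% | about 81% |
| 0.6 | 0.64 | 3.14 | 93% | about 82% |

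Simulated with no treatment effect, the rule's one-sided size is about 4.3-4.9% over this range, so it is slightly conservative.

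**4. T4 regression with the T1 outcome score included.** Assumed: T1-T4 correlation 0.6, and PCL-5 with T1 score 0.5/0.6/0.7, paired with r = 0.4/0.5/0.6. With the T1 score alone, v = 1 - 0.36 = 0.64 and power is 93.0%. The squared partial correlation of PCL-5 with T4 given T1 is (r - 0.6q)^2 / [0.64(1 - q^2)], where q is the PCL-5 to T1 correlation:
- r = 0.4, q = 0.5: 0.10^2 / 0.480 = 0.021; power 93.4%.
- r = 0.5, q = 0.6: 0.14^2 / 0.410 = 0.048; power 94.0%.
- r = 0.6, q = 0.7: 0.18^2 / 0.326 = 0.099; power 95.0%.

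The gain from PCL-5 is about 0.4, 1 and 2 points.

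**5. T1-T4 change contrast (1B.1).** With equal variances at the two times, change variance is 2 - 2 x 0.6 = 0.8. The covariance of PCL-5 with change is r - q = -0.1 in all three scenarios, so R^2 = 0.01 / 0.8 = 1.25%. Power moves from 87.4% to 87.7%, about 0.4 points (change-score approximation to the mixed model).

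**The case against.** The strongest reply is that most of the headline gain belongs to a different gap. The rise from about 81-82% to 86/89/93% exists because the T4 regression omits the T1 score of the outcome. Put that score in, and PCL-5 adds two points at most under these assumptions. The T1 PDRI score also already carries its own PTSD subscale. This stands and limits the point.

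Second, the analytic plan lists PTSD, mood disorder, anxiety and TBI history as candidate covariates, so it does not fully carry through the denial in the design section, and it never cites that denial as the reason for its entry rule. This also stands. The entry rule still gives a listed predictor no route into the Hypothesis 1B models unless the arms differ on it.

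Third, no correlation of PCL-5 with any primary outcome is given, and the Rationale reports higher problem levels rather than prediction of T4 scores. The figures are therefore conditional on the assumed range.

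A reader might also infer more than the text supports:
- **That the trial is biased for want of stratification, or that error is inflated.** Randomisation protects the comparison, and the rule's size is at or just below nominal.
- **That the same contradiction covers TBI or age.** The Rationale passage concerns PTSD and mental health. Background mentions TBI research only as showing a need for programs, and nothing is said about age as a predictor.
- **That precision is lost to a material degree in every Hypothesis 1B test.** For the change contrast the loss is close to nil.

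**Conclusion.** The point holds as an inconsistency about PTSD and psychiatric conditions, together with a covariate rule driven by chance imbalance. It is a matter of efficiency and prespecification.

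For the T4 regression as it stands, prespecifying T1 PCL-5 is worth roughly 5 to 11 power points over the screening rule. That falls to about 0.4-2 points if the T1 outcome score is also included, and is about 0.4 points for the change contrast. These sizes rest on the assumed correlations, an assumed 0.05 screening threshold, 65 effective participants per arm and d = 0.44. The textual conflict and the lack of any prespecified covariate do not depend on those assumptions. The change is worth making because it is nearly free and fixes the model in advance.

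**What to change.** - In section 4(b), correct the stated reason for not stratifying so that it no longer denies an influence of PTSD and psychiatric conditions. Simple randomisation can be defended without it, and the randomisation itself need not change.
- In Statistical Methods by Research Aims and under Hypothesis 1B, replace the whole screen-then-adjust rule. Both conditions must go: removing only the link to treatment group would leave covariates selected on their observed association with outcome, which is still data-driven.
- Name instead a short set, fixed before unblinding and used whatever the baseline balance: the T1 score of the outcome and T1 PCL-5 in the T4 regression. The mixed model already holds the T1 score as a repeated measure and gains almost nothing from PCL-5. TBI history need not be forced into either model.
- Keep the baseline comparison as description only, and report the unadjusted model as a sensitivity analysis.

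The cost is SAP wording and one or two degrees of freedom. Both covariates are already collected at T1.
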